## 9.4 Analyses of the Secondary Endpoints

The analysis population for the following analyses will be the ITTI Population unless otherwise specified.

- 1) Proportion of patients positive for influenza virus titer and virus RNA by RT-PCR
  - The proportion of patients positive for influenza virus titer/virus RNA (RT-PCR) at each scheduled time point will be calculated. The 95% CIs will be calculated by the Clopper-Pearson method.
  - The Mantel-Haenszel test with baseline composite symptom score ( $\leq 11$  or  $\geq 12$ ) and region (Japan/Asia, Rest of the world) as stratification factors will be used to compare these endpoints between two groups at each scheduled time point.
- 2) Change from baseline in virus titer and in the amount of virus RNA (RT-PCR)
  - The summary statistics for the change from baseline in virus titer and in the amount of virus RNA (RT-PCR) will be presented by treatment group at each scheduled time point.

- Van Elteren test with baseline composite symptom score ( $\leq 11$  or  $\geq 12$ ) and region (Japan/Asia, Rest of the world) as stratification factors will be used to compare these endpoints between two groups at each scheduled time point. The p value for the Van Elteren test is defined as the p value for “Row Mean Scores Differ” in the “Alternative Hypothesis of Cochran-Mantel-Haenszel Statistics”, using the following SAS code.  
[Example: Comparison between the S-033188 group and the placebo group]  

```
proc freq data= analysisdata;  
  table REGION*SCOREC*TRTP*VARIABLE / cmh2 scores=modridit  
  noprint;  
  where TRTP in ("S-033188", "Placebo");  
run;
```

    - SCOREC: Category of Baseline composite symptom score ( $\leq 11$  or  $\geq 12$ )
    - TRTP: Treatment group
    - VARIABLE: Response variable
- 3) Area under the curve adjusted by baseline in virus titer and in the amount of virus RNA (RT-PCR)
- The similar analyses for the change from baseline in virus titer and the amount of virus RNA will be performed with the area under the curve adjusted by baseline as the response variable.
- 4) Time to cessation of viral shedding by virus titer/by virus RNA
- The patients with a positive virus titer/the amount of virus RNA on Day 1 (i.e., patients whose virus titer/the amount of virus RNA is equal to the lower limit of detection or higher) will be included in the following analysis.
- The similar analyses for the primary endpoint (Section 9.1.1.1, 9.1.1.2 and 9.1.1.3, excluding analyses of PPS population) will be performed with time to cessation of viral shedding by virus titer/RT-PCR. The seed of bootstrapping will be used 16010832.
- 5) Proportion of patients whose symptoms has been alleviated
- The proportion of patients whose symptoms has been alleviated at each scheduled time point will be calculated. The 95% CIs will be calculated by the Clopper-Pearson method.
  - The Mantel-Haenszel test with baseline composite symptom score ( $\leq 11$  or  $\geq 12$ ) and region (Japan/Asia, Rest of the world) as stratification factors will be used to compare these endpoints between two groups at each scheduled time point.
- 6) Time to alleviation of the 4 systemic symptoms/3 respiratory symptoms
- The similar analyses for the primary endpoint (Section 9.1.1.1, 9.1.1.2 and 9.1.1.3, excluding analyses of PPS population and 95% CI for group difference in median time) will be performed with time to alleviation of the 4 systemic symptoms/3 respiratory symptoms.

7) Change from baseline in composite symptom score

- The summary statistics for the change from baseline in composite symptom score will be presented by treatment group at each scheduled time point.
- Analysis of covariance (ANCOVA) with baseline composite symptom score and region (Japan/Asia, Rest of the world) as covariates will be used to compare the change from baseline in the composite symptoms score between two groups at each scheduled time point.
  - The least squares mean (LSM) change and its standard error of means (SE) in each group, the difference between two groups in LSM change, SE, and 95% CI, and p values will be calculated.

[Comparison between the S-033188 group and the placebo group]

```
proc mixed data= analysisdata;  
class REGION TRTP;  
model CHG = TRTP bSCORE REGION /cl;  
lsmeans TRTP;  
estimate "S-033188 vs Placebo" TRTP 1 -1/cl;  
run;
```

- TRTP: Treatment group
- CHG: Change from baseline in the composite symptoms score
- bSCORE: Composite symptoms score at baseline

[Comparison between the S-033188 group and the Oseltamivir group]

```
proc mixed data= analysisdata;  
class REGION TRTP;  
model CHG = TRTP bSCORE REGION /cl;  
lsmeans TRTP;  
estimate "S-033188 vs Oseltamivir" TRTP 1 -1/cl;  
run;
```

- TRTP: Treatment group
- CHG: Change from baseline in the composite symptoms score
- bSCORE: Composite symptoms score at baseline

8) Time to resolution of fever

- An analysis similar to that for the primary endpoint (Section 9.1.1.1, 9.1.1.2 and 9.1.1.3, excluding analyses of PPS population) will be performed with the time to resolution of fever as the response variable. The seed of bootstrapping will be used 16010833.

- 9) Proportion of patients reporting normal temperature
  - An analysis similar to that for the proportion of patients positive for influenza virus titer and by RT-PCR will be performed with the proportion of patients reporting normal temperature.
- 10) Body temperature by time point
  - An analysis similar to that for the change from baseline in composite symptom score will be performed with the body temperature. Body temperature at baseline will be added to the covariates in performing ANCOVA.
- 11) Time to alleviation of individual symptoms
  - The similar analyses for the primary endpoint (Section 9.1.1.1, 9.1.1.2 and 9.1.1.3, excluding analyses of PPS population and 95% CI for group difference in median time) will be performed with time to alleviation of individual symptoms.
- 12) Time to return to preinfluenza health status
  - The similar analyses for the primary endpoint (Section 9.1.1.1, 9.1.1.2 and 9.1.1.3, excluding analyses of PPS population and 95% CI for group difference in median time) will be performed with time to return to preinfluenza health status.
- 13) Incidence of influenza-related complications
  - The incidence of each complication (hospitalization, death, sinusitis, otitis media, bronchitis, and radiologically confirmed pneumonia) and its 95% CI will be calculated by treatment group. The 95% CIs will be calculated by the Clopper-Pearson method.
  - Fisher's exact test will be used will be used to compare incidence between two groups for each complication.

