### 9.1.1 Analyses of Primary Endpoint

#### 9.1.1.1 Primary Analysis

Time to alleviation of symptoms will be compared between the S-033188 group and the placebo group using the stratified Peto-Prentice's generalized Wilcoxon test with composite symptoms score at baseline ( $\leq 11$  or  $\geq 12$ ) and region (Japan/Asia or Rest of the world) as stratification factors. Patients who do not experience alleviation of symptoms will be censored at the last observation time point. If at least one of the 7 influenza symptom scores is missing at date and time of assessment that patients have, missing assessments of influenza symptoms conservatively will be treated as having moderate or severe symptoms (as failures) at the corresponding date and time of assessment.

[Comparison between the S-033188 group and the placebo group]

```
proc lifetest data = analysisdata;
  where TRTP in ("S-033188", "Placebo");
  time TIME * CENSOR (0);
  strata SCOREC REGION / group = TRTP test = PETO ;
run;quit;
```

- TRTP: Treatment group
- TIME: Time to alleviation of symptoms

- SCOREC: Category of baseline composite symptom score ( $\leq 11$  or  $\geq 12$ )
- REGION: Category of region (Japan/Asia or Rest of the world)

The same analysis in PPS will be performed as a sensitivity analysis.

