- The summary statistics for change in the index value and change in VAS score will be presented by treatment group at each scheduled time point.

5) Work Productivity Questionnaire

- The summary statistics for the percentage of absenteeism due to influenza illness and the percentage of work productivity loss due to influenza illness will be presented by treatment group.
- For Question 4 in Work Productivity (WP) Questionnaire, the summary statistics for the number of days required for personal assistance will be presented by treatment group. One day is equal to 24-hours.

6) Intrahousehold infection rate

Let  $K$  be the total number of patients included in this analysis,  $y_k$  be the number of  $k^{\text{th}}$  patient's household members infected between Day 1 and Day 15, and  $n_k$  be the number of  $k^{\text{th}}$  patient's household members uninfected by Day 1 ( $k = 1, \dots, K$ ). Under the assumption that  $y_k$  is distributed according to Poisson distribution with mean  $\mu_k$ , the following Poisson regression model will be applied;

$$\log(\mu_k) = \log(n_k) + \beta_0 + \beta_1 x_k$$

In the model,  $x_k$  is a group indicator variable for the  $k^{\text{th}}$  patient, i.e.,  $x_k = 1$  for the S-033188 group,  $x_k = 0$  for the control group (the placebo group or the oseltamivir group). The  $\beta_0$  is an intercept parameter,  $\beta_1$  is a regression parameter. Intrahousehold infection rates for the S-033188 group and the control group are given by  $\exp(\beta_0 + \beta_1)$  and  $\exp(\beta_0)$ , respectively. Estimate and 95% CI of intrahousehold infection rate of each treatment group and comparison between two treatment groups will be carried out using the following SAS code. In addition, a risk ratio of the S-033188 group to the control group and the corresponding 95% CI will be estimated by the above Poisson regression model.

```
Data analysisdata;  
  set analysisdata;  
  lnum=log(NUM);  
run;
```

[Comparison between the S-033188 group and the placebo group]

```
proc genmod data = analysisdata;  
  class TRTP;  
  model RES = TRTP / dist = poisson link = log offset = lnum;  
  lsmeans TRTP / cl exp;  
  estimate "S-033188 vs Placebo" TRTP 1 -1 / exp;  
run;
```

- NUM: Number of household members uninfected by Day 1
- TRTP: Treatment group (1:S-033188, 2:Placebo)
- RES: Number of household members infected between Day 1 and Day 15

[Comparison between the S-033188 group and the Oseltamivir group]

```

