proc genmod data = analysisdata;  
  class TRTP;  
  model RES = TRTP / dist = poisson link = log offset = lnum;  
  lsmeans TRTP / cl exp;  
  estimate "S-033188 vs Oseltamivir" TRTP 1 -1 / exp;  
run;
```

- NUM: Number of household members uninfected by Day 1
- TRTP: Treatment group (1:S-033188, 3:Oseltamivir)
- RES: Number of household members infected between Day 1 and Day 15

The similar Poisson regression model will be applied using the number of household members  $y_k$  infected during each of the following time periods as a response variable;

- From Day1 to Day 3
- From Day 1 to Day 4
- From Day1 to Day 6
- From Day 1 to Day 11

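### The two ANCOVA blocks in SAP 9.4 7) differ only in their ESTIMATE label, so the printed code does not reliably give the contrasts it names

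*SAP*

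**What the plan says.** SAP 9.4 7) specifies an ANCOVA to "compare the change from baseline in the composite symptoms score between two groups at each scheduled time point". It asks for LS means by group and for the between-group difference with SE, 95% CI and p-value. Two code blocks follow.

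- The placebo block ends in "estimate 'S-033188 vs Placebo' TRTP 1 -1/cl" and the oseltamivir block in "estimate 'S-033188 vs Oseltamivir' TRTP 1 -1/cl".
- Both declare "class REGION TRTP" with no ordering option. The variable key reads only "TRTP: Treatment group", with no values and no order.
- Neither block has a WHERE statement.

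SAP 9.4 10) applies a similar analysis to body temperature, with baseline temperature added as a covariate.

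Elsewhere the SAP codes the same variable in two ways.

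- As text: the primary analysis code in SAP 9.1.1.1 contains "where TRTP in ('S-033188', 'Placebo", and the van Elteren code in SAP 9.4 2) has the same filter.
- As numbers: the Poisson blocks in SAP 9.5 6) give "TRTP: Treatment group (1:S-033188, 2:Placebo" for one comparison and "TRTP: Treatment group (1:S-033188, 3:Oseltamivir" for the other, with the same `1 -1` coefficients.

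The opening of SAP section 9 limits every efficacy comparison with oseltamivir to the 20 to 64 years stratum.

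**The concern.** An ESTIMATE statement applies its coefficients by position. `TRTP 1 -1` means first level minus second level, whatever the label says. Two blocks that fit the same model to the same data with the same coefficients must give the same number, yet these carry two different labels. Where the SAP wants two arms in the primary and van Elteren code, it writes the filter into the procedure; here it does not.

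The LSMEANS statement requests no differences, so ESTIMATE is the line that supplies the required difference, SE and CI. If it addresses the wrong levels, the report shows either another comparison under the S-033188 label or the right comparison with its direction reversed. The first changes the estimate, CI and p-value. The second makes a larger fall in symptom score on S-033188 read as a smaller one.

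**Working it through.** The documents give no figure to reproduce. The check is which arms the coefficients pick out under each reading the SAP allows.

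**Inputs.** Coefficients (1, -1), with 0 for any third level: SAP 9.4 7). Text coding: SAP 9.1.1.1 and 9.4 2). Numeric coding 1 = S-033188, 2 = placebo, 3 = oseltamivir: the two keys in SAP 9.5 6) taken together. Assumption from outside the documents: without an ordering option, SAS sorts text class levels alphabetically and unformatted numeric levels by value. A numeric TRTP carrying a text format would sort like text.

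**Level order.** Text gives Oseltamivir < Placebo < S-033188. Numeric gives S-033188 < placebo < oseltamivir.

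**Contrast.** L = 1 × (LS mean of first level) - 1 × (LS mean of second level).

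| Coding | Arms in data | Block labelled v placebo returns | Block labelled v oseltamivir returns |
|---|---|---|---|
| Text | three | oseltamivir - placebo (wrong) | oseltamivir - placebo (wrong) |
| Text | two | placebo - S-033188 (sign reversed) | oseltamivir - S-033188 (sign reversed) |
| Numeric | three | S-033188 - placebo (correct) | S-033188 - placebo (wrong) |
| Numeric | two | S-033188 - placebo (correct) | S-033188 - oseltamivir (correct) |

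**Illustration.** One simulated data set, fitted with treatment, baseline score and region. It assumes mean changes of -8.0 (S-033188), -6.0 (placebo) and -7.5 (oseltamivir) and residual SD 3, with the planned adult ITTI numbers 350, 175 and 350 from Protocol 9.2. The means and SD are invented; the mapping in the table does not depend on them.

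| Coding, arms | Labelled v placebo (95% CI) | Labelled v oseltamivir (95% CI) |
|---|---|---|
| Text, three | -1.61 (-2.15 to -1.08) | -1.61 (-2.15 to -1.08) |
| Text, two | +2.05 (1.51 to 2.59) | +0.44 (0.01 to 0.88) |
| Numeric, three | -2.06 (-2.59 to -1.53) | -2.06 (-2.59 to -1.53) |
| Numeric, two | -2.05 (-2.59 to -1.51) | -0.44 (-0.88 to -0.01) |

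In the two-arm rows the p-values agree between codings: 3.8 × 10⁻¹³ for placebo and 0.047 for oseltamivir. In the numeric three-arm row the line labelled v oseltamivir carries p = 8.8 × 10⁻¹⁴, which belongs to the placebo comparison.

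**Reach.** SAP 9.2 13) lists 11 time points for composite symptom score and SAP 9.2 16) lists 7 for body temperature. (11 + 7) × 2 comparisons = 36 estimates: 11 × 2 = 22 with printed code and 7 × 2 = 14 by cross-reference.

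**Age.** A two-arm filter alone does not apply the 20 to 64 restriction. Planned S-033188 ITTI patients are 62 aged 12 to 19 and 350 aged 20 to 64 (Protocol 9.2), so 62 / (62 + 350) = 62 / 412 = 15% of that arm would fall outside the stated stratum if the data were not also cut by age.

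**The case against.** The strongest reply is that the snippets are model specifications, not production programs, and that data selection is left to the text. This has support. The ANCOVA is to be run at each time point, yet the code has no time-point selection; the bootstrap code in SAP 9.1.1.3 serves two comparisons without a filter; and the text of SAP 9.4 7) says two groups. The Poisson blocks are the only others with an ESTIMATE statement, and they share the two-block layout and the `1 -1`. If their numeric coding is the model for the ANCOVA, both labels are right. The data set name settles nothing, because `analysisdata` is used with both codings.

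That is enough to defeat three stronger readings.

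- A reader might infer that both comparisons are wrong under the SAP's own treatment coding. The SAP has two codings, and under the numeric one with two arms neither is wrong.
- A reader might infer that the oseltamivir comparison is not limited to adults. The opening of SAP section 9 limits it; only the code omits the filter.
- A reader might infer that the Poisson analysis has the same fault. Its keys list exactly two arms per block, and with the data cut to those arms its contrasts are correct.

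It is also fair that a pure sign reversal leaves the two-sided p-value and CI width unchanged and would show against the printed LS means, and that identical output under two labels should be noticed.

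The reply does not close the point. Granting the two-arm cut, the result still depends on a coding that SAP 9.4 7) does not state, and the other code within section 9.4 uses text values, which give the reversed sign.

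**Conclusion.** The point holds as a defect of specification. The printed ANCOVA code does not reliably produce the contrasts it labels: one of the four readings gives both correctly, and that one needs a coding taken from another section plus a filter that is not printed. The documents do not show that any result will be wrong, because the stated intent is clear and a careful programmer could recover it.

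The consequence ranges from none (numeric, two arms), through reversed direction with inference otherwise intact (text, two arms), to the wrong comparison under one label (numeric, three arms) or both (text, three arms). The 36 estimates are an upper bound on what could be affected, and the 14 for body temperature depend on the programmer reusing the printed code. Only secondary endpoints are involved; the primary analysis and the hierarchical comparison with oseltamivir on the primary endpoint are untouched. The conclusion rests on default SAS level ordering, which the SAP does not state.

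**What to change.** 1. State one TRTP coding and one level order, and use them in every code block of the SAP.
2. Add a two-arm WHERE statement to each ANCOVA and Poisson block, as SAP 9.1.1.1 and 9.4 2) already do.
3. Carry the 20 to 64 years restriction from the opening of SAP section 9 into each oseltamivir block.
4. Match the ESTIMATE coefficients to the level order. With two-arm text coding, `-1 1` gives S-033188 minus control; with S-033188 ordered first, `1 -1` is right. Alternatively, request LSMEANS differences with a named reference arm, which removes the dependence on position.
5. State that the same code, with the added covariate, applies to body temperature.

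The cost is a few lines of SAP code. Data, design, model and sample size do not change.

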9.2 Determination of Sample Size

The required sample size of the intention to treat infected (ITTI) population will be 968 (93 patients in 12 to 19 years age stratum and 875 patients in 20 to 64 years age stratum). It is assumed that the RT-PCR positive rate will be 65%. Therefore, 1494 patients (144 patients in 12 to 19 years age stratum and 1350 patients in 20 to 64 years age stratum) will be randomized to ensure an adequate number of patients in the ITTI population. The number of randomized patients may change based on the percentage of patients who are RT-PCR positive during the study.

Rationale for the target sample size:

The primary analysis will be to compare time to alleviation of symptoms between the S-033188 group and the placebo group (both age strata combined).

The median times to alleviation of symptoms in the three placebo-controlled clinical trials of oseltamivir were 116.5, 103.3 and 93.3 hours in the placebo group, respectively [5, 9, 10]. Taking this into account, it was assumed that the median time to alleviation of symptoms in the placebo group will be 100 hours.

In the Phase 2 study for the otherwise healthy patients with influenza virus infection, the median time to alleviation of symptoms was 49.5 hours (95% CI: 44.5, 64.4) in the 40-mg group versus 77.7 hours (95% CI: 67.6, 88.7) in the placebo group. The difference in the median time between 40-mg and placebo was 28.2 hours.

Based on the difference in the Phase 2 study, the difference between the S-033188 group and the placebo group is assumed to be 28 hours (72 hours in the S-033188 group, 100 hours in the placebo group). If the ratio of the median time to alleviation between the S-033188 group and the placebo group remains the same (ie, 0.64: 49.5/77.7) in the proposed study, the difference can further be assumed to be 36 hours (64 hours in the S-033188 group, 100 hours in the placebo group).

The required sample size has been calculated based on the conservative assumption of a 28 hour difference in the median time to alleviation of symptoms between the S-033188 group and the placebo group to ensure at least a 90% power in the efficacy evaluation and to accumulate a larger safety database [12].

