Patients will be randomized on a 2:1 basis to either S-033188 or placebo and a follow-up period will be 336 hours (14 days). Assuming that time to alleviation follows an exponential distribution, the study requires 618 patients as the ITTI population, for the S-033188 group and the placebo group in total, in order for the stratified generalized Wilcoxon test to have 90% or more power with a two-sided significance level of 0.05. Assuming that the percentage of the number of patients in 12 to 19 years age stratum is 15%, the required breakdown will be 62 patients for the S-033188 group and 31 patients for the placebo group in 12 to 19 years age stratum, 350 patients for the S-033188 group and 175 patients for the placebo group in 20 to 64 years age stratum.

Comparison vs oseltamivir: Using a 1:1 randomization ratio between the S-033188 and oseltamivir, ITTI population of oseltamivir will be 350 patients to compare time to alleviation of symptoms between the S-033188 and the oseltamivir in 20 to 64 years age stratum. Table 9-1 shows the statistical power to compare between the S-033188 group and the oseltamivir group under several sets of difference in time to alleviation of symptoms.

Table 9-1 Statistical Power to Compare between S-033188 and Oseltamivir

Median time to alleviation of symptoms (S-033188 group, oseltamivir group)	Statistical power for comparison between the S-033188 group and the oseltamivir group by stratified generalized Wilcoxon test
(72 hours, 84 hours)	42.1%
(70 hours, 84 hours)	54.8%
(68 hours, 84 hours)	67.4%
(66 hours, 84 hours)	78.5%
(64 hours, 84 hours)	87.2%

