## 6.2 Statistical Tests

All statistical tests will be performed at the 0.05 significance level using two-sided tests, unless otherwise noted.

The primary endpoint will first be compared between the S-033188 and placebo groups (primary analysis). Together with the primary efficacy analysis, comparison between the S-033188 and the oseltamivir groups (secondary analysis) will be conducted. For the submission to countries other than Japan, only if statistically significant difference will be observed in primary analysis, secondary analysis will be performed in order to maintain control of overall Type I error.

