Patients who do not experience alleviation of symptoms by the last observation time point will be censored at that time point. If at least one of the 4 influenza symptom scores is missing at date and time of assessment that patients have, missing assessments of influenza symptoms conservatively will be treated as having moderate or severe symptoms (as failures) at the corresponding date and time of assessment.

11) Time to alleviation of the 3 respiratory symptoms (unit: hours)

The endpoint is the time to alleviation of the 3 respiratory symptoms (cough, sore throat, and nasal congestion), which is defined as the time between the initiation of the study treatment and the alleviation of influenza symptoms. The alleviation of the 3 symptoms is defined as the time when all of the 3 respiratory symptoms have been assessed by the patient as 0 (None) or 1 (Mild) in the patient eDiary, for a duration of at least 21.5 hours (24 hours – 10%). Patients who do not experience alleviation of symptoms by the last observation time point will be censored at that time point. If at least one of the 3 influenza symptom scores is missing at date and time of assessment that patients have, missing assessments of influenza symptoms conservatively will be treated as having moderate or severe symptoms (as failures) at the corresponding date and time of assessment.

12) Time to alleviation of individual symptoms (unit: hours)

Time to alleviation of cough symptom is defined as the time from the start of treatment to the start of the time period when cough symptom have been assessed by the patient as 0 (None) or 1 (Mild) in the patient eDiary, for a duration of at least 21.5 hours (24 hours – 10%). The following endpoints are defined in a similar way. Patients who do not experience alleviation of symptoms by the last observation time point will be censored at that time point. If symptom score is missing at date and time of assessment that patients have, missing assessment of influenza symptom conservatively will be treated as having moderate or severe symptoms (as failures) at the corresponding date and time of assessment.

Patients whose symptom at baseline is assessed as 0 (None) or 1 (Mild) will be excluded from the analysis.

- Time to alleviation of sore throat symptom
- Time to alleviation of headache symptom
- Time to alleviation of nasal congestion symptom
- Time to alleviation of feeling feverish or having chills symptom

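### The fever and individual-symptom tests do not stratify by the endpoint's own baseline, which is collected; they stay valid but can lose a little power

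*SAP*

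**What the plan says.** The primary test is a stratified Peto-Prentice generalized Wilcoxon test, coded in SAP 9.1.1.1 as "strata SCOREC REGION / group = TRTP test = PETO", that is, composite score category and region. SAP 9.4 then reuses it:

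- **Item 8), time to resolution of fever:** an analysis like the primary one "will be performed with the time to resolution of fever as the response variable".
- **Item 11), time to alleviation of individual symptoms:** the same test.
- **Item 9), proportion with normal temperature:** refers back to the Mantel-Haenszel test of item 1), with the same two factors.

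Protocol 9.10.3.2, items 9, 10 and 12, names the same two factors for these endpoints.

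SAP 6.5.2 defines the baseline for both temperature and symptom scores. In these three analyses it is used only for exclusion. SAP 9.2 14) and 15) drop patients whose baseline temperature is below 37°C. For individual symptoms SAP 9.2 12) says: "Patients whose symptom at baseline is assessed as 0 (None) or 1 (Mild) will be excluded from the analysis".

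For body temperature by time point, SAP 9.4 10) goes further: "Body temperature at baseline will be added to the covariates in performing ANCOVA". Protocol 9.10.3.2, item 11, lists only composite score and region for that ANCOVA, and SAP section 14 does not record the addition.

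**The concern.** For the primary endpoint, the composite score is the endpoint's own baseline, so stratifying on it makes sense. Carried over to fever, it is a weak substitute. It sums seven self-rated symptoms, only one of which (feverishness or chills) concerns temperature, and is then cut in two. For a single symptom, the score contains that symptom's grade, but diluted among six others.

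Leaving a prognostic baseline out of a rank-based survival test mixes fast and slow recoverers within each stratum. This pulls the apparent treatment effect towards the null and costs power. It does not create false positives, because randomization still balances the omitted factor on average. What is at stake is the sensitivity of some secondary comparisons. It matters more against oseltamivir, where the plan's power table for the primary endpoint considers smaller differences than against placebo.

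**Working it through.** **Inputs from the documents**
- SAP 6.2: "All statistical tests will be performed at the 0.05 significance level using two-sided tests, unless otherwise noted".
- Protocol 9.2: "the study requires 618 patients as the ITTI population" (412 + 206), for the test "to have 90% or more power with a two-sided significance level of 0.05", with assumed medians "72 hours in the S-033188 group, 100 hours in the placebo group".
- Protocol 9.2: exponential times, 336 hours of follow-up, and 350 v 350 for the oseltamivir comparison.

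**Inputs that are assumptions (not in the documents)**
- Half the patients have the worse own baseline (for a symptom: severe rather than moderate).
- Composite score ≥12 occurs in 70% of these and in 30% of the others.
- The score itself has a recovery-hazard ratio of 0.8.
- 25% of patients are from Rest of the world.
- The own-baseline hazard ratio h (worse v better) runs from 1.0 to 0.33.
- Sample sizes and medians are borrowed from the primary endpoint, because none are given for these endpoints.

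**Step 1: reproduce the plan's figures.** Let λ = ln 2/median, p₁ and p₀ the allocation shares, Y₁ = p₁e^(−λ₁t), Y₀ = p₀e^(−λ₀t) and S = Y₁ + Y₀. With survival weights and integrals from 0 to 336 hours:

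z = √N × ∫ S·[Y₁Y₀/(Y₁+Y₀)]·(λ₁−λ₀) dt ÷ √( ∫ S²·[Y₁Y₀/(Y₁+Y₀)²]·(Y₁λ₁+Y₀λ₀) dt ), and power = Φ(z − 1.96).

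- 412 v 206, 72 v 100 hours: z = 3.243, power 90.0%. The plan states 90% or more.
- 350 v 350, oseltamivir median 84 hours, S-033188 median 72, 70, 68, 66, 64: z = 1.759, 2.080, 2.410, 2.749, 3.098, power 42.1, 54.8, 67.4, 78.5, 87.2%. These equal all five entries of protocol Table 9-1 (SAP Table 1).

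**Step 2: add the own baseline.** Times are exponential with hazard (ln 2/m₀) × (m₀/m₁)^treatment × h^(x−0.5) × 0.8^(c−0.5). Here m₁ and m₀ are the S-033188 and control medians, x is the own baseline (0/1) and c the score category (0/1). Each simulated trial is tested by stratified Peto-Prentice with score × region (4 strata) and with score × region × own baseline (8 strata), 10,000 trials per cell. Power in %, without → with the own-baseline stratum:

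| h | 350 v 350, 66 v 84 h | 350 v 350, 70 v 84 h | 412 v 206, 72 v 100 h |
|---|---|---|---|
| 1.0 | 78.5 → 78.2 | 54.5 → 53.8 | 90.1 → 89.6 |
| 0.8 | 78.2 → 78.1 | 54.5 → 54.5 | 89.8 → 89.7 |
| 0.67 | 77.1 → 78.0 | 52.8 → 53.6 | 89.2 → 89.9 |
| 0.5 | 74.5 → 77.6 | 50.1 → 53.0 | 87.6 → 89.8 |
| 0.33 | 68.5 → 77.1 | 44.9 → 52.6 | 82.3 → 88.7 |

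For 66 v 84 hours the change is −0.3, −0.1, +0.9, +3.1 and +8.6 points. The standard error of one power near 78% is √(0.78 × 0.22/10,000) = 0.4 point.

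**Step 3: Mantel-Haenszel (item 9).** With 412 v 206, control proportion 50%, treatment odds ratio 1.7 (both outcome inputs assumed) and 5,000 trials, own-baseline odds ratios of 1, 1.5, 2 and 4 give 86.0 → 85.9, 86.4 → 86.4, 84.2 → 85.2 and 78.6 → 81.7%.

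**Step 4: type I error.** With no treatment effect and h = 0.5, the rejection rate is 5.3% without and 5.1% with the extra stratum (412 v 206, 3,000 trials), and 5.0% for both at 350 v 350 (10,000 trials).

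**The case against.** The case for leaving the plan alone is substantial. The two factors are those the protocol names for these endpoints, and both were used in randomization. The documents state no power for these endpoints, which lie outside the hierarchy, so no planned power is lost. The exclusions already use part of the own baseline, leaving grades 2 and 3, or at least 37°C. And a linear covariate in an ANCOVA is nearly free, whereas each added factor in a stratified test multiplies the strata, so item 10) does not oblige the SAP to change items 8), 9) and 11). All of this stands, and it makes the point one of efficiency and not of error. It does not remove the point: item 10) shows that the protocol's factor list was not treated as closed, and going from 4 to 8 strata costs little at these sample sizes.

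Two stronger readings are tempting. A reader might infer that the tests are invalid or biased towards a false positive; step 4 shows no such effect.

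A reader might also infer a loss of 8 to 10 points. If the baseline is taken as continuous, independent of the score and split into tertiles, a correlation ρ with log time of 0.4 or 0.5 takes power at 66 v 84 hours from 66% to 74% or from 61% to 71%. The documents do not support so strong a predictor. At ρ = 0.4 the slope is (π/√6) × 0.4/√(1 − 0.16) = 0.56 per standard deviation. The outer tertiles of a normal variable lie about 2.18 standard deviations apart on average, so the top tertile would take e^(0.56 × 2.18) ≈ 3.4 times as long to recover as the bottom one. That model also ignores the overlap between the score and a symptom's own grade.

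**Conclusion.** The point holds as a small, optional efficiency gain. The planned tests are valid. Adding the own baseline changes power by about 0 points if it is weakly prognostic (hazard ratio 0.8 or closer to 1, with a cost of up to about 1 point if it is not prognostic at all). The gain is about 1 point at 0.67, 2 to 3 points at 0.5, and 6 to 9 points only at 0.33 (8 to 9 in the 66 v 84 hour case).

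These figures rest on an assumed prognostic strength and on the primary endpoint's medians and sample sizes. They illustrate the size and do not predict it. Individual-symptom analyses drop patients with grade 0 or 1, so their absolute power would be lower than shown at the same effect. For fever the gain is probably at the low end, because entry requires at least 38°C, which narrows the range of baseline temperature.

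**What to change.** - **SAP 9.4 11):** add the baseline grade of the symptom analysed (2 or 3) as a third stratification factor.
- **SAP 9.4 8) and 9):** add baseline temperature in two categories, split at the median of the blinded pooled ITTI distribution. SAP 6.5.2 accepts a baseline temperature only under diary set-up and same-day conditions, so some patients may have none. Keep them in the analysis in a prespecified category, so that they do not fall out of the stratified test.
- **All three:** keep score and region, retain the two-factor test as a sensitivity analysis, and leave the primary test unchanged.
- **SAP section 14:** list the change and its reason, since protocol 9.1 requires departures to be explained in the SAP. The covariate already added in 9.4 10) belongs there too.

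The cost is SAP wording, one derived variable and one more stratification variable per test. Strata rise from 4 to 8 (12 where the missing-temperature category is populated), with up to about 1 point of power lost if the baseline is not prognostic, and the factor list then differs between endpoints.
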